## 9.3.3 Analysis of the Secondary Endpoint(s)

NA

### 9.3.4 Adherence and Retention Analyses

The analysis will follow the intention-to-treat (ITT) principle and include data from every subject irrespective of whether the subject was compliant with the assigned intervention. A quantitative assessment of compliance with the intervention, ranging from 0 (complete non-compliance) to 1 (full compliance), will be included as a weighting factor to allow more compliant subjects to contribute more to the analysis. The weight for the control phase will be set to 1 since subjects are not required to exercise.

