### CONFIDENTIAL

This material is the property of the NYU School of Medicine and Langone Medical Center. Do not disclose or use except as authorized in writing by the study sponsor Drug/Device Template Version: 13 JUN 2016

Statistical Analysis	The analysis will follow the intention-to-treat (ITT) principle and include data from every subject irrespective of whether the subject was compliant with the intervention. A quantitative assessment of compliance with the intervention, ranging from 0 (complete non-compliance) to 1 (full compliance), will be included as a weighting factor to allow more compliant subjects to contribute more to the analysis.
----------------------	---

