Like all longitudinal studies, exercise intervention studies are at risk of losing participants who choose to discontinue their participation during the intervention. Our team has developed effective strategies to promote high levels of adherence even with this challenging population, with our preliminary studies showing low attrition rates [23, 24]. Our previous experience with intervention studies indicates that the main reason patients discontinue participation is the cost associated with travel (bridge/tunnel tolls, parking, bus, and taxi fare). Therefore, we have budgeted funds to offset transportation expenses for participants (up to \$20 per visit). To further convenience our participants, we will offer flexible scheduling for appointments in our research dedicated physical therapy center ([name]), including availability 5-days/week and 12-hrs/day (from 8am to 8pm). In the current proposal, data analysis will follow the ITT principle and include data from every subject regardless of whether the subject complied with the intervention.

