# 9.3 Description of Statistical Methods

A weighted paired sample *t*-test will be used to assess whether each outcome changed from baseline to follow-up as a result of the exercise intervention. Weighted analysis of covariance (ANCOVA) will be used to compare the time points in terms of the change in each outcome. The change in each outcome from baseline to follow-up will be the dependent variable and the ANCOVA model will include the matching factors (age, baseline MNSI) and the measure of general activity level as numeric covariates and the binary indicator of intervention as a classification factor. The secondary objective is to assess the extent to which exercise induced improvements in DTI outcomes are mediated or explained by reduction in ROS. After testing the effect of the intervention on the change in DTI and the correlation between changes in DTI and ROS, an incomplete causal pathway meditational analysis will be conducted using the method of Baron and Kenny[63] with a bootstrap based test of the indirect (mediation) effect of ROS. The exploratory objective to identify baseline factors (e.g., age, MNSI, general activity) predictive of improvement, represented as the baseline to follow-up change in each outcome, will be addressed using linear regression and bivariate correlations. This analysis will be stratified by intervention and then conducted using data from both intervention groups combined. In each case, the assessment of compliance will be included as a weighting factor.

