# 9.3.2 Analysis of the Primary Efficacy Endpoint(s)

A matched-pairs Wilcoxon signed rank test will be applied to the within-subject change in each outcome among subjects demonstrating full compliance with the exercise program. Additionally, weighted analysis of covariance (ANCOVA) will be used to test the change in each outcome adjusting for the measured level of compliance using data from all subjects. The values of each outcome at

CONFIDENTIAL

baseline and follow-up for all subjects will be the dependent variable and the ANCOVA model will include time (baseline versus follow-up) as the within-subject factor of interest covariates, the measure of compliance as numeric covariate and an anonymized subject ID as a classification factor so that the comparison of times will be based on their within-subject difference. The secondary objective is to assess the extent to which exercise induced improvements in DTI outcomes are can be at least partially explained by reduction in ROS will be addressed using linear regression, The baseline to follow-up change in each outcome will be the dependent variable and the model will include the measure of compliance as a numeric factor and the within-subject change in ROS as the numeric factor of interest. A second regression will be conducted with baseline factors (e.g., age, MNSI, general activity) added to the model in order to identify factors predictive of improvement in each outcome.

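### The plan promises an intention-to-treat result, but every named test of the exercise effect is weighted by compliance or restricted to full compliers, and compliance is never defined

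*Combined protocol and SAP*

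**What the plan says.** The ITT commitment appears three times. The Protocol Summary states: "The analysis will follow the intention-to-treat (ITT) principle and include data from every subject irrespective of whether the subject was compliant with the intervention". Section 1.2 says that "data analysis will follow the ITT principle and include data from every subject regardless of whether the subject complied with the intervention". Section 9.3.4 repeats it. Section 9.4 then claims 80% power with 40 subjects analysed on that principle.

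In both the Protocol Summary and Section 9.3.4, the next sentence introduces the weight: "A quantitative assessment of compliance with the intervention, ranging from 0 (complete non-compliance) to 1 (full compliance), will be included as a weighting factor". Its stated purpose is to let more compliant subjects count for more. Section 9.3.4 fixes the control-phase weight at 1.

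Four tests of the exercise effect are named:

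1. Section 9.3: "A weighted paired sample *t*-test will be used to assess whether each outcome changed from baseline to follow-up".
2. Section 9.3: "Weighted analysis of covariance (ANCOVA) will be used to compare the time points in terms of the change in each outcome".
3. Section 9.3.2: "A matched-pairs Wilcoxon signed rank test will be applied to the within-subject change in each outcome among subjects demonstrating full compliance".
4. Section 9.3.2: "weighted analysis of covariance (ANCOVA) will be used to test the change in each outcome adjusting for the measured level of compliance". This model uses all subjects and contains time, compliance as a numeric covariate, and subject ID as a classification factor.

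Section 5.1.2 lists signs of inadequate fidelity but gives no rule for scoring them. Sections 4.7.2 and 12.3 use 80% attendance only to pro-rate payment.

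**The concern.** An ITT estimate counts each participant once, whatever exercise they completed. A weight equal to later compliance discards that. A participant scored 0 contributes nothing to the exercise effect, and one who stops early contributes little if the score reflects sessions completed. Section 4.7.2 ends participation after more than one consecutive missed week, so low scores are foreseeable.

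The result then describes participants in proportion to their adherence. It is too high if compliance and improvement go together (simple dose-response is enough), unbiased if they are unrelated, and too low if they run in opposite directions. The protocol would report this estimate under the ITT name and would have powered a different test.

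Because the score and the full-complier set have no definition, both could be settled after outcomes are seen. Full compliance could mean all 30 sessions (3 a week for 10 weeks, Section 5.1.1), sessions meeting every criterion in Section 5.1.2, or, at the loosest, the 24 of 30 sessions that mark the 80% payment threshold.

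**Working it through.** **1. Which test does the power statement describe?** Inputs are the baseline means in Table 3 and the exercise change SDs in Table 4, with n=40 and two-sided 5%. For an unweighted paired test, the detectable change at 80% power is (1.960 + 0.842) × SD / √40:

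- BOLD: 2.802 × 1.26 / 6.325 = 0.558, and 0.558 / 3.24 = 17.2% of baseline.
- PCr: 2.802 × 12.85 / 6.325 = 5.69, and 5.69 / 41.16 = 13.8%.
- MNSI: 2.802 × 1.78 / 6.325 = 0.788, and 0.788 / 5.2 = 15.2%.

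All three lie in the stated 10% to 18%. The power claim is that of an unweighted test in 40 subjects, which the plan does not contain.

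**2. Weighted paired t-test under dose-response.** The documents give no compliance distribution, so the following are assumptions. Let c be compliance and let change be proportional to c. The weighted mean is then proportional to E(c²)/E(c) and the all-subjects mean to E(c), so the excess is E(c²)/E(c)² − 1.

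The rejection columns assume instead a true mean change of zero and a non-causal compliance-change correlation of 0.3 (n=40, 40,000 simulated trials per row, nominal 5%). The plan names no variance estimator, so model-based and robust results are both shown.

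| Assumed compliance | Mean | Excess | Rejection, model-based / robust |
|---|---|---|---|
| Beta(9,1) | 0.90 | 1.0% | 5.3% / 5.4% |
| Beta(4,1) | 0.80 | 4.2% | 6.7% / 6.5% |
| 10% uniform on 0–0.5, rest uniform on 0.8–1 | 0.835 | 6.2% | 8.0% / 7.5% |
| 20% uniform on 0–0.5, rest uniform on 0.8–1 | 0.77 | 12.6% | 11.4% / 9.9% |
| Beta(2,1) | 0.67 | 12.5% | 10.9% / 9.4% |
| Beta(1,1) | 0.50 | 33.3% | 22% / 16% |

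Example for Beta(4,1): E(c²) = (4×5)/(5×6) = 0.667, and 0.667 / 0.64 = 1.042. The unweighted test rejects about 5% of the time throughout. With correlation −0.3 the rejection rates are about the same and the bias is negative. With correlation 0 and robust variance they are 5.0% to 5.8%. Mean compliance alone does not settle the size: 0.835 with a few early stoppers gives more excess than an even 0.80.

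**3. The Section 9.3.2 model.** Assume weight 1 on the baseline row and c on the follow-up row. This is inferred, because Section 9.3.4 gives weight 1 only to the control phase. The coding of the compliance covariate is not stated, and it matters:

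- *Once per subject:* the covariate is redundant with subject ID (42 columns, rank 41). The time effect is a mean change weighted by c/(1+c). Under the same dose-response the excess is 0.6%, 2.7% and 8.9% at mean compliance 0.9, 0.8 and 0.67.
- *Per row (1 before, c after):* the model has full rank and the time effect is the fitted change at c=1. The excess is 1/E(c) − 1, or 11%, 25% and 50%.

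**4. Is an unweighted primary test affordable?** Standardised changes from Table 4 are MNSI 1.20/1.78 = 0.674, PCr 10.61/12.85 = 0.826 and BOLD 1.11/1.26 = 0.881. Noncentral-t power, two-sided 5%:

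| Setting | MNSI | PCr | BOLD |
|---|---|---|---|
| n=40, Table 4 effects | 98.6% | 99.9% | 99.97% |
| n=40, effects × 0.8 | 91% | 98% | 99% |
| n=32, effects × 0.8 | 84% | 95% | 97% |

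**5. Phase comparison in Section 9.3.** The change-score ANCOVA names no subject term. Control weight 1 against exercise weight 0 to 1 is therefore not a within-person comparison. This is a smaller point.

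**The case against.** The strongest reply is that the difference may be small here. Section 1.2 reports low attrition and high adherence in preliminary studies, sessions are supervised, and payment falls below 80% attendance. At mean compliance of 0.8 to 0.9 with no cluster of early stoppers, the t-test excess is 1% to 4% and null rejection 5.3% to 6.7%. This stands and limits the severity. The larger figures need less even compliance, an assumed correlation, or per-row coding.

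The early-stopper rows also assume that stoppers return for endpoint testing. If they do not, analysed scores are uniform on 0.8 to 1 and the excess among those analysed is 0.00333 / 0.81 = 0.4%. Missing follow-up is then the main problem, and an unweighted test of those with data shares it. This also stands, and it is why the fix needs a missing-data rule.

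The Section 9.3 sentence "In each case, the assessment of compliance will be included as a weighting factor" follows the exploratory analyses and probably governs only those. The finding does not rely on it: tests 1, 2 and 4 are themselves called weighted, and the Protocol Summary and Section 9.3.4 supply the weight.

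Finally, this is a one-group study with no randomisation for ITT to protect, the weighting is openly prespecified, and dropping the ITT label would also remove the contradiction. It would, but the power statement would then need redoing, and the score would still lack a formula. The anchors at 0 and 1 and the fidelity list do not amount to one.

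**Conclusion.** The concern holds, and the plan should be changed. The contradiction rests on the text alone: the ITT result that is promised and powered is produced by none of the four tests, and neither the compliance score nor full compliance has an operational rule.

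The size is conditional. It is negligible to modest for the weighted t-test if compliance is high and even, and about 6% to 13% if 10% to 20% stop early and are still measured. For the Section 9.3.2 model at mean compliance 0.9 to 0.8, it is 11% to 25% if the covariate is coded per row and under 3% if coded once per subject. These figures assume benefit proportional to compliance; the direction reverses if compliance and improvement are negatively related.

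**What to change.** - Name one unweighted within-subject analysis of all enrolled participants with outcome data as primary, for example a mixed model for repeated measures, and state how missing follow-up is handled.
- Label the compliance-weighted and full-complier analyses as supportive.
- Define the 0-to-1 score and full compliance before outcomes are examined.
- Remove the compliance main effect from the Section 9.3.2 model. If dose-response is of interest, make it a separate secondary regression of change on the pre-defined score.
- Add a subject term to the phase comparison in Section 9.3.
- State whether endpoint data are sought from participants terminated under Section 4.7.2. The invitation there and in Section 6.4.5 is worded for those who choose to withdraw.

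The cost is protocol and SAP wording, a scoring rule and a missing-data rule. No added sample size is needed on the Table 4 figures. The reported effect may be smaller, because non-compliers would count fully, and some follow-up may still be missing.

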# 9 Statistical Considerations

# 9.1 Statistical and Analytical Plans

The primary objective is to assess and compare the interventions (exercise versus control phase in the same individual) in terms of the baseline to follow-up change in the following outcomes: 1) DTI, plasma ROS level, and the MNSI assessment of DPN symptoms (Aim 1); and 2) leg mitochondrial function, oxidative capacity (31P-MRI), peak MV response (BOLD-MRI), the proportion of fat-free muscle (IDEAL-MRI) and leg muscle strength (Aim 2).

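### Weight c in the exercise phase, weight 1 in the control phase and no subject term: the planned phase contrast is not a within-person comparison

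*Combined protocol and SAP*

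**What the plan says.** Section 9.1 states the primary comparison as "exercise versus control phase in the same individual". Section 9.3 carries it out with a weighted ANCOVA. "The change in each outcome from baseline to follow-up will be the dependent variable"; the covariates are given by "the ANCOVA model will include the matching factors (age, baseline MNSI) and the measure of general activity level as numeric covariates", and the term of interest is "the binary indicator of intervention as a classification factor". No subject term is listed.

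Section 9.3.4 defines the weights. Compliance, "ranging from 0 (complete non-compliance) to 1 (full compliance), will be included as a weighting factor", is used "to allow more compliant subjects to contribute more to the analysis". For the other phase, "The weight for the control phase will be set to 1 since subjects are not required to exercise".

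Section 9.3.2 does put a subject term in a model: "an anonymized subject ID as a classification factor so that the comparison of times will be based on their within-subject difference". That model contrasts baseline with follow-up, not exercise with control.

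**The concern.** A person with c = 0 counts fully in the control mean and not at all in the exercise mean. With no subject term to tie a person's two changes together, the two means are taken over differently weighted populations. A course that a person would show in both phases then fails to cancel. If people who comply poorly also have a different course, that difference is credited to exercise or held against it.

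A control phase in the same person is there to exclude this kind of between-person difference. The combination of 9.3 and 9.3.4 lets it back in. This is a separate matter from whether compliance weighting is compatible with ITT, and from how the standard error is computed: correcting only the standard error would leave the estimate biased.

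**Working it through.** **Inputs from the plan.** Weights: c and 1 (Section 9.3.4). Model: change on age, baseline MNSI, activity and phase (Section 9.3). n = 40. BOLD change in Table 4: exercise mean 1.11, SD 1.26; control mean 0.18, SD 1.42. BOLD baseline mean in Table 3: 3.24.

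**Assumed, because the plan gives no figures.** Compliance mean and SD of 0.9 and 0.1, 0.8 and 0.2, or 0.7 and 0.3. Correlation r of compliance with personal trend, after covariates, 0.3 or 0.5. Trend SD 0.89 or 1.26, meaning half or all of the variance of the planned exercise change (1.26/√2 = 0.89).

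**Step 1: the plan's own figures.** The detectable BOLD change with 80% power is (1.960 + 0.842) × 1.26/√40 = 0.558, or 17.2% of 3.24. This lies inside the stated 10% to 18%. The anticipated change is 1.11/3.24 = 34.3%, the top of the stated 23% to 34%. The planned phase difference is 1.11 − 0.18 = 0.93, and 0.93/0.18 = 5.2, the number that Section 9.4 prints (with a percent sign) for BOLD. So 0.93 is a fair yardstick. None of these power figures allows for the weighting.

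**Step 2: the contrast as written.** Let E_i and C_i be person i's exercise-phase and control-phase changes. Leaving covariates aside, weighted least squares with only a phase indicator gives

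Σc_iE_i/Σc_i − mean(C_i).

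**Step 3: its expectation with no exercise effect.** Let each person have a trend s_i that is the same in both phases. Then

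E[contrast] = Σc_is_i/Σc_i − mean(s_i) = Cov(c, s)/mean(c) = r × SD(s) × SD(c)/mean(c).

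Toy check: 20 people have c = 1 and s = 1, and 20 have c = 0.2 and s = 0. The exercise mean is 20/(20 + 4) = 0.833 and the control mean is 0.500, a spurious effect of 0.333.

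**Step 4: size for BOLD** (in brackets, as a percentage of 0.93).

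| Mean c, SD c | r | Trend SD 0.89 | Trend SD 1.26 |
|---|---|---|---|
| 0.9, 0.1 | 0.3 | 0.030 (3.2%) | 0.042 (4.5%) |
| 0.9, 0.1 | 0.5 | 0.049 (5.3%) | 0.070 (7.5%) |
| 0.8, 0.2 | 0.3 | 0.067 (7.2%) | 0.095 (10.2%) |
| 0.8, 0.2 | 0.5 | 0.111 (12.0%) | 0.158 (16.9%) |
| 0.7, 0.3 | 0.3 | 0.114 (12.3%) | 0.162 (17.4%) |
| 0.7, 0.3 | 0.5 | 0.191 (20.5%) | 0.270 (29.0%) |

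**Step 5: what makes the trend cancel.** With one weight per person in both phases, the contrast is Σc_i(E_i − C_i)/Σc_i, and s_i drops out. It also drops out if a subject factor is added while the weights stay at c and 1: the estimate is then a weighted mean of E_i − C_i with person weight c_i/(1 + c_i). The fault therefore needs both parts, unequal weights and no subject term.

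**Step 6: simulation check** (n = 40, 1,500 runs per case, no exercise effect, BOLD SD 1.26 with half the variance a shared trend, three noise covariates). With weights c and 1 and no subject term, the mean spurious effect was:

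- 0.038 for compliance 0.9 and 0.1, latent correlation 0.5
- 0.060 for 0.8 and 0.2, correlation 0.3
- 0.099 for 0.8 and 0.2, correlation 0.5
- 0.159 for 0.7 and 0.3, correlation 0.5
- 0.002 for 0.8 and 0.2 when compliance was unrelated to trend.

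The first four lie somewhat below the closed form with trend SD 0.89, because compliance is bounded and the correlation was set on a latent scale. With a subject factor, or with one weight per person, the result was −0.002 to 0.005 (Monte Carlo standard error 0.005).

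**The case against.** **The weights alone do not cause the bias.** A reader might infer that the weight sentence in 9.3.4 is by itself enough. It is not: Step 5 shows that a subject factor cancels a common trend even with weights c and 1. This stands. It does not rescue the plan, because the subject ID in 9.3.2 belongs to a different contrast and the 9.3 phase model lists none.

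**It is unclear which model governs.** The section titled as the primary efficacy analysis is 9.3.2, and 9.3.5 says there will be no comparison between groups. That is a real ambiguity. Sections 2.1 and 9.1 nevertheless set exercise against control phase as the primary objective, and only the 9.3 model addresses it.

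**The reach is limited.** In Attachment A only MRI (weeks 1, 5 and 18) brackets the control phase. MNSI is scheduled at weeks 0, 1 and 18, bloodwork at weeks 1 and 18, and calf performance at weeks 7 and 16. Table 4 gives no control value for MNSI. This stands: on that schedule the phase contrast cannot be formed for those outcomes. Section 9.3.1 counts only two imaging visits, but Sections 1.2 and 3.1 agree with Attachment A on three.

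**A large bias favouring exercise is not established.** A reader might infer one, on the ground that poor compliers are sicker. Suppose 25% of people have c = 0.2, the rest 0.95, and the low compliers' trend is worse by one change SD (about 1.34). Low compliers then carry 25% of the control mean and 0.05/0.7625 = 6.6% of the exercise mean. The bias is 0.184 × 1.34 = 0.25, or 27% of 0.93. Nothing in the documents supports those inputs. Section 4.7.2 treats more than one consecutive missed week as termination (though such people may still have endpoint testing), and Section 1.2 reports low attrition in preliminary studies. With 20% at c = 0.6 and the same trend gap, the low compliers' shares are 20% and 0.12/0.88 = 13.6%. The bias is 0.064 × 1.34 = 0.085, or about 9%. The sign is not known either.

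**No type I error rate follows.** A reader might expect an inflated error rate. In the simulation above, ordinary weighted standard errors with no subject term rejected in only 0.9% to 2.9% of runs, because the phase changes were positively correlated. With a correlation of −0.5, which the shared middle scan makes possible, rejection was about 12% even with no bias. The rate depends on a standard error and a correlation that the plan does not give.

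**Conclusion.** The point holds as a flaw in the estimate. As written, 9.3 and 9.3.4 together compare a compliance-weighted exercise mean with an unweighted control mean, and no other section corrects this. With no exercise effect and a trend equal in both phases, the contrast estimates Cov(c, trend)/mean(c), after adjustment for age, baseline MNSI and activity. For BOLD that is about 0.03 to 0.27, or 3% to 29% of the planned phase difference, over compliance and correlation ranges that are assumed. With mean compliance 0.9 and SD 0.1 it is 3% to 8%. If compliance is unrelated to trend it is zero.

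The documents do not support saying that the bias must favour exercise, that it is large, that it affects every outcome, or that the test has a particular false-positive rate. The change is worth making because the plan's stated comparison is lost for no gain, and restoring it costs almost nothing.

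**What to change.** Replace the last sentence of Section 9.3.4 with: *Each participant carries one and the same weight in both phases.* Set that weight to 1 in both phases for the main ITT analysis. In any compliance-weighted sensitivity analysis, analyse the within-person difference E_i − C_i with weight c_i. Adding the subject ID to the 9.3 phase model, with c_i in both phases, gives the same estimate. A person with no exercise-phase change then does not enter the control mean of that analysis.

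The cost is one sentence and one line of code. The downside is that low compliers' control data are also down-weighted in the sensitivity analysis, so it uses slightly less control-phase information.

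The change removes only the bias that comes from the weights. The phases last 4 and 10 weeks, so a trend that grows with time would not cancel under any weighting. That limit should be stated when the phase contrast is interpreted.
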